Common clinical biomarkers related to FD nephropathy (alpha-1-microglobulin, microalbumin, creatinine) will be compared with the pivotal biomarkers associated with the inflammatory and dysregulated immune pathways.

Table 2: Suggested pivotal biomarkers and pathways involved in Fabry nephropathy:

	Relationship to pathway or involvement	Biomarkers	
Inflammatory biomarkers	Cytokines	NF- κ B pathway	IL-1 β , IL-6, TNF- α , IL-10
		TGF- β 1 pathway	TGF- β 1, IL-4, INF-gamma
		TLR4 pathway	IL-18, IL-12
	Chemokines	NF- κ B pathway	MCP1, IL-8, RANTES, BAFF , APRIL
		TLR4 pathway	PAI-1
Biomarkers of kidney function and proteinuria	clinical laboratory urine biomarkers	alpha-1-microglobulin, albumin, cystatin C, GFR	
	We will measure in our laboratory	B2M, bikunin, NGAL, osteopontin, clusterin, creatinin.	
Acute kidney injury	Marker of renal tubular injury	KIM-1	
	Inflammation-associated glycoprotein	YKL-40	
	Growth factor, fibrosis	EGF	
	Apoptotic marker	CK-18 M30	
	Pyroptotic markers	IL-1β, IL-18 (included in the list of cytokines)	

This is a study to assess the markers related to autophagy, apoptosis, pyroptosis, and inflammatory markers related to NFkB, TNF-alpha, and TGF-β1 pathways in the urine. Urinary biomarkers will then be compared to the standard measures of kidney function and proteinuria: GFR, cystatin-C, B2M, bikunin, NGAL. Gb3 and Lyso-Gb3, urine microalbumin, and urine protein-to-creatinine (UPCR) ratio. We will also analyze the role of therapy, especially for the inflammatory responses in patients on stable enzyme replacement therapy (ERT) with that of patients naïve to therapy.

OBJECTIVE AND SPECIFIC AIMS

Primary objective: Identify biomarkers in urine for the detection and progression of kidney involvement in naïve male and female patients with FD, and compare with patients on ERT to assess the effects of ERT.

Specific Aims:

- 1) *To identify urinary inflammatory biomarkers associated with nephropathy in FD.*
- 2) *Analyze the association between urinary inflammatory markers, clinical urine biomarkers, circulating lyso-Gb3, and kidney involvement in naïve FD patients.*
- 3) *Analyze the association between urinary inflammatory markers, clinical urine biomarkers, circulating lyso-Gb3, and kidney involvement in FD patients on stable ERT.*

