- 4) *Assess the role of the time of initiation and duration of therapy (ERT), respectively, inactivation and reversibility of inflammation cascade, and how these relate to the degree of kidney involvement in patients with FD.*

SUBJECT SELECTION

Number of Subjects

A total of 50 subjects, male or female, between the ages of 18 to 80 years of age, include 25 healthy individuals and 25 patients with Fabry disease.

Study population

FD patients n=25 (5 without clinical evidence of nephropathy and 15 patients with clinical evidence of nephropathy), NAÏVE FD patients (n=5), and healthy controls n=25 (controls, urine samples are not actual patients, urine samples will be purchased from a commercial company).

The study will involve 50 age-and gender-matched subjects and controls divided into the following cohorts:

1. FD subjects without clinical evidence of nephropathy (normal eGFR and no microalbuminuria) naïve or on ERT (**n=5**),
2. FD subjects with clinical evidence of nephropathy (**n=15**)
 Subcohorts:
 - a. FD subjects on ERT with CKD stage 1 (estimation n=5)
 - b. FD subjects on ERT with CKD stage 2 (estimation n=5)
 - c. FD subjects on ERT with CKD type 3 a or b (estimation n=5)
3. FD patients naïve to therapy (**n=5**). Can we be included in Cohort group 1 or 2.
 Additional analysis will be stratified NAÏVE vs. ERT.
4. Non-FD age-matched controls with no known kidney disease n=25.

	FD	Healthy control
Total FD	25	25
without nephropathy	5	
with nephropathy	15	
NAÏVE	5	

Table 3. Clinical staging of FD patients:

Clinical parameter(s)	FD patients and kidney involvement				Age-matched controls
	Stage 1	Stage 2	Stage 3a	Stage 3b	
Kidney involvement					
Kidney damage	Normal/	Mild reduction	Moderate reduction	Moderate reduction	normal
GFR ml/m1.73 m ²	>90	60-89	45-59	30-44	90 min
Cystatin-C	0.5-0.9	1.0-1.2	1.3-1.5	1.4-1.9	0.5-0.9
Urine B2M	-	0.428-0.603	0.603-0.950	0.950-1.034	-
FD biochemical markers					
α-Gal A	Deficiency	Deficiency	Deficiency	Deficiency	Normal
GLA mutations	Yes	yes	yes	yes	No
Gb-3	Yes	yes	yes	yes	No
Lyso-Gb-3	Yes	yes	yes	yes	No

Gender of Subjects

Subjects of both genders will be included in the research, and it is expected that this inclusion will be representative of the FD patients population.

Age of Subjects

Subjects will be between the age of 18 to 80 years of age.

Racial and Ethnic origin

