Events/issues which are part of the study objectives or endpoints will be systematically identified and collected from healthcare records or other applicable source records and summarized as part of any interim analysis and in the final study report. Such events do not need to be notified as individual reports to Takeda Pharmacovigilance.

Events/Issues which are not part of the study objectives and endpoints will not be abstracted or collected from healthcare records or other applicable source records.

Reporting of Adverse Drug Reactions to Regulatory Agencies and IRB/EC

LDRTC is responsible for reporting serious and non-serious adverse drug reactions suspected of being related to regulatory authorities. The Investigator is responsible for reporting adverse drug reactions to the IRB/EC, if required by national law or regulation, within the timelines required by such law or regulation. The Investigator shall maintain records of all such submissions.

Study-specific committees

No steering committee, data safety monitoring committee, or clinical endpoint committee will be used in this study.

STUDY OVERSIGHT

Premature Termination of Study:

[name], may prematurely terminate the study. Reasons for termination may include but is not limited to the following:

- Series of adverse events or incidences associated with subject participation.
- Low subject enrollment.

Clinical Research Quality Assurance:

To ensure that GCP and good clinical research are conducted per regulatory requirements and guidelines, the study will be made available for monitoring, auditing, review, and inspection by regulatory authorities such as IRB and FDA. This will be accomplished by providing direct access to study-related documents.

Data management

The acquired data will be entered into Excel for further analysis. Data will be analyzed using GraphPad Prism software (Graphpad Inc., La Jolla, CA) using ANOVA analysis and Student's t-test for statistical analysis. $p < 0.05$ is considered significant.

Samples and data storage

Once subjects have signed the informed consent form, they will be assigned a personal generic research study identification number. This number will be matched with the patient's name and demographic information in a file stored on a password-protected computer. Only members of the research team at **Lysosomal & Rare Disorders Research & Treatment Center, Inc** will have

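### The named methods, ANOVA and Student's t-test, do not estimate the continuous associations in Aims 2 to 4 (urinary markers with circulating lyso-Gb3, unbanded markers, and ERT start and duration)

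*Protocol*

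**What the plan says.** The statistical methods stand in one sentence of the protocol, under Study Oversight, Data management: the data go into GraphPad Prism and are analysed "using ANOVA analysis and Student's t-test for statistical analysis", with p < 0.05 as the criterion. No other method is named elsewhere in the protocol.

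The aims ask for more than group comparisons. Specific Aims 2 and 3 are to "Analyze the association between urinary inflammatory markers, clinical urine biomarkers, circulating lyso-Gb3, and kidney involvement", in naïve patients and in patients on stable ERT respectively. Aim 4 is to "Assess the role of the time of initiation and duration of therapy (ERT") in relation to the inflammation cascade and the degree of kidney involvement. The Brief Rationale and Background adds: "Urinary biomarkers will then be compared to the standard measures of kidney function and proteinuria: GFR, cystatin-C, B2M, bikunin, NGAL", and then "Gb3 and Lyso-Gb3, urine microalbumin, and urine protein-to-creatinine (UPCR) ratio".

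Several groups are defined. Study population gives Fabry versus control, nephropathy yes/no and the CKD-stage subcohorts, and it states "Additional analysis will be stratified NAÏVE vs. ERT". Study design and plan adds a UPCR threshold of 0.5 g/g and the staging in Table 4.

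**The concern.** ANOVA and the t-test compare means between groups. They answer an aim when one of the two quantities is already a group. When both are continuous, they give neither a coefficient nor a measure of strength, and they can be applied only once one of the two has been cut into categories.

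For several of the pairs in Aims 2 to 4 the protocol supplies no categories. An analyst who keeps to the stated methods would have to choose cut-points, possibly after seeing the data, and would lose information in a sample where little can be spared. Three of the four specific aims are touched, each in part.

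**Working it through.** **1. Which parts of the aims have groups to work with**

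| Quantity | Groups among Fabry patients in the protocol | Served by ANOVA or t-test? |
|---|---|---|
| Kidney involvement by GFR | CKD stages 1, 2, 3a, 3b (Tables 3 and 4) | Yes |
| Kidney involvement by UPCR | Cut at 0.5 g/g | Yes |
| Nephropathy yes/no; naïve vs ERT | Yes (Study population) | Yes |
| Cystatin-C | Bands overlap: 3a 1.3–1.5, 3b 1.4–1.9 | Not cleanly |
| Urine B2M | No Stage 1 band | Not cleanly |
| Lyso-Gb3, Gb3 | Marked present in every Fabry stage | Only as an outcome compared across the groups above |
| Bikunin, NGAL | None | Only as an outcome |
| ERT start, ERT duration | None | Only as an outcome |
| Urinary inflammatory markers | None | Only as an outcome |

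Any pair with a defined group on one side is covered. For example, lyso-Gb3 or ERT duration can be compared across CKD stages. A pair drawn from the last four rows has no group on either side. These are inflammatory marker with lyso-Gb3, with Gb3, bikunin or NGAL, and with ERT start or duration.

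**2. How many patients inform these pairs**

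Cohort 2 has n = 15, in subcohorts all described as on ERT. Cohort 1 has n = 5 and is "FD subjects without clinical evidence of nephropathy (normal eGFR and no microalbuminuria) naïve or on ERT". Cohort 3 has n = 5, naïve. If the cohorts are disjoint:
- Fabry total: 5 + 15 + 5 = 25, which agrees with the stated total.
- On ERT: 15 + (0 to 5) = 15 to 20.
- Naïve: 5 + (0 to 5) = 5 to 10.

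The protocol leaves open whether cohort 3 overlaps cohorts 1 and 2, so these counts are an assumption.

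**3. Illustration of what grouping would cost**

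The protocol gives no correlation, so ρ is assumed and a range is shown. Data are simulated as y = ρx + √(1 − ρ²)·e, with x and e independent standard normal, two-sided α = 0.05 and 100,000 runs per cell. Relative loss = 1 − (median-split power ÷ comparator power).

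| n | ρ | Median-split t | Spearman | Pearson | Loss vs Spearman | Loss vs Pearson |
|---|---|---|---|---|---|---|
| 15 | 0.3 | 0.133 | 0.175 | 0.193 | 24% | 31% |
| 15 | 0.5 | 0.312 | 0.439 | 0.501 | 29% | 38% |
| 15 | 0.7 | 0.626 | 0.807 | 0.876 | 22% | 29% |
| 15 | 0.8 | 0.810 | 0.941 | 0.975 | 14% | 17% |
| 20 | 0.3 | 0.169 | 0.227 | 0.256 | 25% | 34% |
| 20 | 0.5 | 0.423 | 0.570 | 0.640 | 26% | 34% |
| 20 | 0.7 | 0.788 | 0.918 | 0.955 | 14% | 18% |
| 20 | 0.8 | 0.932 | 0.987 | 0.996 | 6% | 6% |

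**4. What any method can deliver at these sizes**

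Fisher-z 95% CI for an assumed observed r of 0.5: tanh(atanh(0.5) ± 1.96/√(n − 3)), with atanh(0.5) = 0.549.
- n = 5: −0.68 to 0.96
- n = 10: −0.19 to 0.86
- n = 15: −0.02 to 0.81
- n = 20: 0.07 to 0.77

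At 5 to 10 naïve patients, Aim 2 is descriptive whatever the method.

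**5. Number of tests**

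Table 2 lists 15 inflammatory markers. Against three predictors (lyso-Gb3, ERT start, ERT duration) that makes 15 × 3 = 45 tests, and 45 × 0.05 = 2.25 chance positives would be expected if none were truly related.

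**The case against.** The methods sentence does not say that nothing else will be used, and an analysis plan that is not shown may name a correlation. Silence on a method would not be a fault in a protocol. Here, however, the protocol does state its methods, and they leave part of its own aims unserved. That part of the objection softens the point without removing it.

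A reader might also infer that lyso-Gb3, ERT start and ERT duration can be tested only after ad hoc grouping. The documents do not support this. Each can be the outcome in an ANOVA across CKD stages or a t-test across UPCR strata, and Aim 4 itself refers to the degree of kidney involvement. The gap is confined to pairs with no group on either side.

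Nor should the lyso-Gb3 row in Tables 3 and 4 be read as fixing a binary analysis variable. It sits with enzyme deficiency and mutation status as a disease descriptor, and Setting/Location plans a lyso-Gb3 assay.

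The power figures describe a median split that the protocol does not plan, so they remain illustration. The gain from the fix is also modest in absolute terms. At ρ = 0.3 power stays at 0.18 to 0.26, at n = 15 the interval around r = 0.5 still includes zero, and the study already calls itself descriptive.

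**Conclusion.** The point holds in a limited form. ANOVA and the t-test suit the defined group contrasts and part of Aims 2 to 4. They do not estimate the associations of urinary inflammatory markers with circulating lyso-Gb3, with unbanded markers, or with ERT start and duration, and the protocol gives no cut-points that would turn these into group comparisons.

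This conclusion rests on setting the methods sentence beside the aims and needs no power figure. If the data were grouped by median split, the relative loss of power at an assumed ρ of 0.5 would be 26–29% against Spearman and 34–38% against Pearson for 15 to 20 patients, and less at ρ of 0.7 to 0.8. Those sizes assume bivariate normal data and disjoint cohorts. The amendment is worth making because it is cheap, but it will not make these analyses confirmatory.

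**What to change.** Amend the Data management sentence as follows.

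- Keep ANOVA and t-tests for Fabry versus control, nephropathy yes/no, CKD stage by GFR, UPCR stratum, and naïve versus ERT.
- For inflammatory markers against circulating lyso-Gb3, unbanded markers, ERT start and ERT duration, use Spearman correlation, or regression of the log marker on one continuous predictor at a time, with 95% CIs.
- Use one value per patient (baseline) for the cross-sectional associations, or a mixed model with a patient random effect if the 0, 6 and 12 month samples are analysed together.
- Label these results, and all of Aim 2, as descriptive or exploratory, given the small numbers and the many marker-by-predictor tests.
- Confirm when the circulating lyso-Gb3 value is obtained: Table 5, as shown, lists urine as the only specimen collected.

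The cost is a few lines of text and slightly more analysis, with no extra patients. ERT history is already to be recorded (Demographics and Medical History). If no lyso-Gb3 value is otherwise available, a blood sample may have to be added. There are limits to accept: Spearman gives no slope, log-scale results read as fold-changes, one predictor at a time does not separate ERT start from duration, a baseline-only analysis sets aside the later samples, and many tests at p < 0.05 will produce chance positives.

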Figure 1. Fabry nephropathy. The pathogenesis leads to the activation of inflammatory cascades and fibrosis. The model was adopted from publication (6).

BRIEF RATIONALE AND BACKGROUND

Progressive nephropathy, glomerulosclerosis, tubular atrophy, and interstitial fibrosis are associated with inflammatory cellular infiltration. The Gb-3 accumulation in lysosomes leads to early cellular dysfunction followed by cell death, which activates inflammatory pathways and stimulates tissue fibrosis in Fabry disease. Progressive nephropathy, including glomerulosclerosis, tubular atrophy, and interstitial fibrosis, are associated with inflammatory cellular infiltration in the kidney. While Gb-3 accumulation is primarily located in endothelial and epithelial glomerular cells, histological studies demonstrate that the buildup of Gb-3 in podocytes plays an essential role in glomerular damage (7). Moreover, the study of urine-derived FD kidney epithelial cells and podocytes *in vitro* demonstrates that the cause of this damage lies in deregulated autophagy

pathways (7, 8). Deposition of Gb-3 in glomerular cells leads to focal segmental glomerular sclerosis. In addition, Gb-3 deposition in podocytes leads to activation of necroptosis (Figure 1). Podocyte injury, detachment, and podocyturia might be the initial pathogenic events in FD nephropathy (Figure 1). Gb3 accumulation in podocytes has been shown to resist ERT clearance partially. Moreover, the Gb3 accumulation in lysosomes continuously activates inflammatory pathways and stimulates pathogenetic processes, while the cellular clearance of Gb-3 by ERT limits histological damage.

It is well known that the NF- κ B, TGF- β 1, and Nothch1 signaling pathways play an essential role in nephropathy (Table 1 and 2). Moreover, Gb-3 deposition is associated with the increased release of TGF- β 1 and epithelial-to-mesenchymal cell transition, leading to the over-expression of profibrotic molecules (Figure 1). TLR4 is involved in the initiation of this process leading to renal fibrosis via inflammasome activation in renal epithelial cells and, at the same time, dysregulated immune response (Tables 1 and 2).

Table 1: Urinary inflammatory biomarkers investigated in this study:

	NF-κB pathway	TGF-β1 pathway	TLR4 pathway
Cytokines	IL-6, IL-1 β , TNF- α , IL-10	TGF- β 1, IL-4, INF-gamma	IL-18, IL-12
Chemokines	MCP1, IL-8, RANTES, BAFF , APRIL		plasminogen activator inhibitor (PAI-1)

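### The protocol's only significance rule is an unqualified p < 0.05 on a panel of at least 15 urinary markers, so a marker that passes by chance has the same status as a well-supported one

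*Protocol*

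**What the plan says.** The statistical text of the protocol is in the Data management paragraph under Study Oversight. Data will be analysed "using ANOVA analysis and Student's t-test for statistical analysis", and then "p < 0.05$ is considered significant". The rule is not limited to one marker or contrast, and a marker that passes is not described as nominal.

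The aims are about selecting markers. The primary objective begins "Identify biomarkers in urine for the detection and progression of kidney involvement", and specific aim 1 is "To identify urinary inflammatory biomarkers associated with nephropathy in FD". Study design and plan speaks of establishing novel biomarkers. No primary marker is named, and the protocol does not say when a marker counts as identified.

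The panel is given in two tables. Table 1, headed "Urinary inflammatory biomarkers investigated in this study", lists 15 markers. Table 2 repeats these and adds kidney-function and injury markers. The text after Table 2 treats some of the additions as reference measures: "Urinary biomarkers will then be compared to the standard measures of kidney function and proteinuria: GFR, cystatin-C, B2M, bikunin, NGAL".

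On the other side, Study type calls the study descriptive and observational, and the Urinalysis paragraph calls the laboratory tests exploratory. Neither statement is tied to the p < 0.05 rule.

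**The concern.** A 5% level limits the error of one test. Here the same level serves a whole panel, and the study's main product is a list of markers. As the protocol stands, a reader of the report would see markers called significant with nothing to separate those expected to pass by chance from those with strong support. In a small study of a rare disease (25 patients and 25 controls), chance findings could be carried into further work as established markers of Fabry nephropathy.

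**Working it through.** **No figure to reproduce.** The 0.05 is a stated threshold. The sample size of 50 comes without a power statement, effect size or standard deviation.

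**Step 1: count the markers.**
- Table 1: NF-κB cytokines 4, TGF-β1 cytokines 3, TLR4 cytokines 2, NF-κB chemokines 5, PAI-1 1. Total 4 + 3 + 2 + 5 + 1 = 15.
- Table 2, one reading: add KIM-1, YKL-40, EGF and CK-18 M30 (4), and osteopontin and clusterin (2), leaving B2M, bikunin and NGAL as comparators. Total 15 + 4 + 2 = 21.
- Table 2, wider reading: add all 4 injury markers and all 6 markers measured in the study laboratory. Total 15 + 4 + 6 = 25.

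**Step 2: expected chance passes per contrast, no true differences.** The formula is 0.05 × m. It holds whatever the correlation, and equally for one omnibus ANOVA per marker.

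**Step 3: chance of at least one such pass.** The formula is 1 − 0.95^m for independent markers. For correlated markers it was simulated with equal correlations between test statistics (200,000 draws). The correlations are assumed.

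| Markers (m) | Expected passes | At least one, independent | Correlation 0.5 | Correlation 0.7 |
|---|---|---|---|---|
| 15 | 0.75 | 54% | 36% | 26% |
| 21 | 1.05 | 66% | 43% | 30% |

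**Step 4: some markers truly differ (illustration only).** Assume that 5 markers differ by 1 SD, that markers are independent, and that each is tested once by t-test. Four group splits were simulated. 25 vs 25 is Fabry against control. 15 vs 5 is nephropathy against none, from the cohort sizes. 15 vs 10 and 20 vs 5 are the same contrast with the five naïve patients added to the group without or with nephropathy; 20 vs 5 also serves for ERT against naïve if all other patients are on ERT.

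| Split | Mean false share at p < 0.05, 15 markers | 21 markers |
|---|---|---|
| 25 vs 25 | 8% | 13% |
| 15 vs 5 | 16% | 23% |
| 15 vs 10 | 12% | 18% |
| 20 vs 5 | 15% | 22% |

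With other assumptions (2, 5 or 10 true markers; 0.5, 1 or 1.5 SD; 15 or 21 markers), the share runs from about 2% to 55%. The top value comes from few true markers, a small effect and low power.

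**Step 5: what a fixed 10% false discovery rate would do.** The assumptions are those of step 4, with 21 markers. Entries are mean numbers of markers.

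| Split | True markers found: p < 0.05, then 10% rate | True lost | False removed | Runs with nothing identified at 10% |
|---|---|---|---|---|
| 25 vs 25 | 4.7, then 4.4 | 0.3 | 0.3 | under 1% |
| 15 vs 5 | 2.2, then 1.0 | 1.2 | 0.6 | about 40% |
| 15 vs 10 | 3.2, then 2.2 | 1.1 | 0.5 | 14% |
| 20 vs 5 | 2.4, then 1.2 | 1.2 | 0.6 | about 35% |

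In the three small splits the fixed cut-off loses about twice as many true markers as it removes false ones.

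**The case against.** The strongest reply is that a protocol normally states a nominal level and leaves adjustment to the SAP, which is not at hand. The Data management sentence says only what is significant and does not say that a significant marker is identified. An SAP could add q-values without contradicting it. This stands in part: the absence of a multiplicity method would not by itself be a finding. What remains is that the protocol itself states an unqualified rule beside an aim to identify and establish markers, and offers no other standard of evidence for that claim.

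The second reply is that the study is exploratory. That is right as far as it goes. A reader might infer that family-wise error must be controlled, but the documents do not support this for a study described as descriptive and observational.

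The third reply is that p < 0.05 is not the only criterion in the document. This stands. Study design and plan gives a GFR slope, a UPCR limit and staging cut-offs, and aims 2 and 3 look at association with lyso-Gb3 and kidney involvement. The slope, UPCR and staging cut-offs classify patients, however; they do not say how strong the evidence for a marker must be.

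The fourth reply is that 21 is a choice, since Table 2 puts osteopontin and clusterin in the same row as B2M, bikunin and NGAL. This also stands. The firm count is the 15 of Table 1.

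**Conclusion.** The point holds in a limited form and is worth fixing. An unqualified p < 0.05 is applied to at least 15 markers in a study meant to select markers. If none truly differs, 0.75 (15 markers) to 1.05 (21 markers) pass per contrast. This rests only on the marker count and on one valid 5% test per marker. The chance of at least one pass depends on correlation and lies between 26% and 66% over the cases computed.

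Two stronger readings should be resisted. A reader might infer from the 2% to 55% range that up to half of the reported list will be false. The protocol gives no effect sizes, so that range reflects assumptions and does not predict this study. A reader might also infer that a fixed false discovery rate must decide which markers count as identified. In the small patient contrasts that is a trade-off which can lose more than it gains.

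Where the five naïve patients are counted ("Can we be included in Cohort group 1 or 2", followed by "Additional analysis will be stratified NAÏVE vs. ERT") affects the size of the patient contrasts. It is a separate question, and this point does not depend on it. Nothing here invalidates the study.

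**What to change.** Amend the significance sentence in Data management so that:
- p < 0.05 is described as nominal and hypothesis-generating;
- the panel to which q-values apply is listed, with comparators such as B2M, bikunin and NGAL kept apart;
- for every marker in that panel and every contrast, the report gives the raw p-value, the Benjamini-Hochberg q-value across the panel, and the effect size with its confidence interval;
- wording such as identified or established rests on the q-value and not on p < 0.05 alone.

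A fixed cut-off such as 10% is optional. If one is chosen, the loss of true markers in the small contrasts should be acknowledged and nominal markers should stay in the report.

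The cost is a few sentences and a few lines of analysis. Claims for some markers will be slightly weaker. No marker, sample or visit is dropped.
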